Child Rearing Inventory (CRI)	X	X	X	The CRI is an 11-item parent report measure of tolerance for child misbehavior.	Parent Report
Parental Satisfaction Scale	X	X	X	Questionnaire designed to assess parents' attitudes toward parenting. It has 3 subscales: Satisfaction with Spouse/Ex-Spouse Parenting Performance, Satisfaction with the Parent-Child Relationship, and Satisfaction with Parenting Performance.	Parent-Report
Acceptance and Action Questionnaire-II	X	X	X	Measures psychological acceptance in parents of children with disabilities	Parent

Measure	When Assessed	Description	Type of Measure
Process Variables			
Attendance	Taken at each group session	Yes/no was the participant at session	Group leader
Treatment evaluation form	Completed by parents at 4 th and last session	Measure of treatment satisfaction and program evaluation	Parent-Report
Ratings of primary stressors	Completed by parents at 1 st , 4 th and last session	Parents list their top 3 stressors and rank how stressful they are on a scale from 1 to 10.	Parent-Report
Five Facets of Mindfulness Questionnaire	Completed at sessions 1, 4, and 8	Self-report inventory for the assessment of general mindfulness skills. Subscales include: Observe, Describe, Act with Awareness, Nonjudge, and Nonreact	Parent-Report
Mindful Parenting Scale	Completed at sessions 1, 4, and 8	Self-report inventory for the assessment of how parenting incorporate mindfulness into their parenting. Subscales include: Observe, Describe, Act with Awareness, Nonjudge, and Nonreact	Parent-Report
Family Information Form (FIF)	X	Family demographic and health history completed as an interview with the parents during the lab visit.	Parent Interview

DATA STORAGE

Usual procedures are used to safeguard participants in this research. All participants are protected by the applicable laws and professional regulations and ethics from disclosures of confidential information. The confidentiality of all information obtained in the study will be protected, and all study personnel will be trained in the strict requirement of not disclosing any information obtained in the study.

To protect confidentiality, data will be coded by subject number rather than name, and all identifying information will be kept separate from the data. All hard copies of instruments will be kept in a locked storage cabinet that is kept in a locked room within a locked research building. In addition, all hard copy and electronic data will be stored by identification number only. Electronic copies of the data will be stored on computers and servers with strong passwords for future analyses. Data will only be saved in a secure location on the LLU server. If a portable device (e.g. laptop) is used at any point in the study, the device will be encrypted, data will only be stored on the device temporarily, and the device will be stored in a physically secure location (e.g. locked in laboratory room). Access to the data is restricted to authorized study personnel. Data will be retained in locked files until it is clear that no further analyses will be done.

The informed consent form states that information about the family cannot be released to anyone other than the consenting parent unless the investigators have signed written permission. The informed consent form states that information about the child can be released only if the investigators learn of physical or sexual abuse of the child or the investigators learn that someone is in imminent danger of harm. There is no plan to release data to any agency. Information provided by one study participant (mother, father, teacher, youth) will not be shared with any other participants.

These stringent safeguards are likely to be effective and will remain to fully protect the participants, with very little likelihood of risk.

DATA ANALYSIS

Data analysis will primarily use parametric statistics to examine (1) whether there is a significant reduction in parenting stress as a result of the intervention (e.g. dependent sample t-tests), (2) whether there is a significant reduction in children behavior problems as a result of the intervention (e.g. dependent sample t-tests), (3) whether parenting behavior mediates the relationship between reductions in parenting stress and subsequent reductions in child behavior problems (e.g. hierarchical multiple regression and univariate analysis of variance), and (4) whether the impact of the intervention on parenting stress and/or children behavior problems changes as a function of the specified modifying variables (e.g. hierarchical multiple regression and univariate analysis of variance). Hierarchical Linear Modeling (HLM) may be employed after the project is completed to examine growth trajectories of the variables of interest over time.

POTENTIAL RISKS AND DISCOMFORTS

Risks for participants are minimal. All procedures for this study have been used widely in previous research, with little to no discomfort or risk to either the parents or the child. Nevertheless, some of the questions in the questionnaires and interviews do seek personal information, and might be considered an invasion of privacy (e.g. questions about the marriage). Only the parent is asked to provide information and complete questionnaires. The child is not interviewed or asked to complete any measures. However, the child is asked to participate in a play task with the parent(s) and during this task the child might experience some mild frustration (e.g. during the clean-up task). In the PI's experience using these tasks in similar studies, the risks or likelihood of discomfort is minimal. Additionally, if the parent and/or child decide to not complete the assessment (e.g. not complete a questionnaire, refuse to participate in the play assessment) the family will still be compensated for the assessment. The parent(s) and child have the right to refuse to answer any question or terminate their involvement in the study at any time.

In order to minimize risks, participants will be free to choose not to respond to any item or participate in any activity they find potentially objectionable. The PI (who is a clinical psychologist) will be available at all times to address any concerns subjects may have. The assessment will not be longer than 40 minutes in order to minimize demands on the parent and child. However, parents and children will also be able to take breaks as needed. Additionally, in the event that an assessment needs to be rescheduled, the family will be compensated upon completion of the rescheduled assessment. Finally, as described above, if the parent and/or child decide to not complete the assessment once the assessment as already begun (e.g. not complete a questionnaire, refuse to participate in the play assessment) the family will still be compensated for the assessment. However, if the family withdraws from the study before completion, they will not receive the remaining payments.

BENEFITS

Potential benefits to the family include: (1) possible reduction in parental stress and improvement in parents' mental health following the intervention, (2) possible decline in children's behavior problems and improvement in their social competence following the intervention, and (3) possible increase in positive parenting behavior and decrease in negative/intrusive parenting behavior following the intervention. Additionally, families will have access to specialists in child development, the opportunity to learn more about their children's abilities through the laboratory assessment, and receipt of feedback about their children's behavioral development after the intervention is completed.

Benefits to society include the identification of intervention programs that may help reduce parental stress and child behavior problems, both of which are a significant concern among families of children with developmental delays. Furthermore, this study may help to elucidate the processes that pose risk for children with developmental delays, as well as identify processes that serve as protective factors for these children's emerging abilities. More specifically, we will examine the mechanisms through which parental stress and mental health problems impact the development of children's behavioral difficulties and this information can be used to further develop preventive intervention programs for children and families.

COMPENSATION

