Informed consent will be obtained at the first laboratory assessment. Parents will be given the informed consent form (see included consent form) and asked to read the form. If the parent prefers, the experimenter will read the form to the parent. The experimenter will also provide a summary of study (e.g. timeline for intervention, expectations with regard to pre, post and follow up assessments, compensation, components of assessment, and potential risks of study). Parents will be informed that intervention group assignment is random and that they may be assigned to the Spring group (March through April 2012) or the Summer group (June through July 2012). The experimenter will be available to answer any and all questions the parent(s) has and to address any concerns. Parents will be reminded that their consent is voluntary, that they can withdrawal from the study at any point, and that they do not have to answer any question or participate in any task that they do not want to. Given the young age of the children in the study (ages 3 to 5), parents will consent for their own and their child's participation. The PI for this project has had extensive training in conducting research with similar families and has completed the HIPAA compliance training online (certificate is included). Graduate students working on

the project as research assistants have also completed the HIPAA training online and are completing training with the PI on providing informed consent and administering the standardized protocol.

STUDY DESIGN

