Sanders, J. L., & Morgan, S. B. (1997). Family stress and adjustment as perceived by parents of children with autism or down syndrome: Implications for intervention. *Child & Family Behavior Therapy*, 19(4), 15-32.

Singh, N. N., Lancioni, G. E., Winton, A. S. W., Fisher, B. C., Wahler, R. G., McAleavey, K., . . . (2006). Mindful parenting decreases aggression, noncompliance, and self-injury in children with autism. *Journal of Emotional and Behavioral Disorders*, 14(3), 169-177.

Singh, N. N., Lancioni, G. E., Winton, A. S. W., Singh, J., Singh, A. N., Adkins, A. D., & Wahler, R. G. (2010). Training in mindful caregiving transfers to parent-child interactions. *Journal of Child and Family Studies*, 19(2), 167-174.

Yirmiya, N., & Shaked, M. (2005). Psychiatric disorders in parents of children with autism: A meta-analysis. *Journal of Child Psychology and Psychiatry*, 46(1), 69-83.

Objectives

Aim 1: To determine whether MBSR is a feasible intervention with parents of children with developmental delays.

- Hypothesis: The majority of parents (minimum of 60%) who enter the program complete the full 8 weeks of the program. Although we hope for less attrition, this is a conservative estimate given that attrition from child psychotherapy in general is high, ranging from 40% to 60% (Wierzbicki & Pekarik, 1993).

Aim 2: To examine whether MBSR leads to reductions in parenting stress.

- Hypothesis: Parents will self-report significantly lower levels of stress post-intervention and at follow-up.

Aim 3: To investigate whether MBSR is associated with changes in parenting behavior.

- Hypothesis: Parent receiving the intervention will exhibit less negative and intrusive behavior and more positive and sensitive behavior compared to controls as evidenced in observational as well as self-report measures.

Aim 4: To determine whether reductions in parenting stress are associated with decreases in child behavior problems at post-intervention and at follow up.

- Hypothesis: Children of parents receiving MBSR will show greater reductions in behavior problems compared to children of waitlisted parents as evidenced by the participating parent, spouse/significant other, and teacher reports.

Aim 5: To evaluate whether parenting behavior mediates the relationship between parenting stress and child behavior problems.

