Parents assigned to the spring group will begin intervention in March and parents assigned to the summer intervention will begin intervention in June. The intervention will follow the MBSR manual outlined by [name] (Kabat-Zinn et al., 1992). The intervention consists of three main components: (1) didactical material covering the concept of mindfulness, the psychology and physiology of stress and anxiety, and ways in which mindfulness can be implemented in everyday life to facilitate more adaptive responses to challenges and distress, (2) mindfulness exercises during the group meetings and as homework between sessions, and (3) discussion and sharing in pairs and in the larger group. The MBSR program includes eight weekly 2.5 hour sessions, a day-long meditation retreat after class 6, and daily home practice based on audio CDs with instruction. Formal mindfulness exercises include the body scan, sitting meditation with awareness of breath, and mindful movement. MBSR is an empirically supported secular (non-religious) based intervention that can be beneficial to all people. The PI has undergone formal training in MBSR through InsightLA (<http://www.insightla.org>) and has multiple collaborations with formal MBSR teachers. Currently, [name] is planning to deliver the intervention herself; however, if funding permits she will hire a certified MBSR teacher (who will complete HIPAA certification and obtain IRB approval before teaching).

After the completion of the project (all assessments have been conducted) parents will receive a short summary of their child's current and previous behavioral functioning in order to reinforce parents' efforts to improve their parenting skills as well as raise awareness of remaining concerns.

Robinson, E. A., & Eyberg, S. M. (1981). The dyadic parent-child interaction coding system: Standardization and validation. *Journal of Consulting and Clinical Psychology*, 49(2), 245-250.

Measures and Data Collection

See table below for information on measures and data collection time points (pre-intervention, post-intervention, and follow-up)

Measures for MAPS Program (Mindful Awareness & Parenting Stress)

Measure	Pre-Tx	Post-Tx	Follow-Up	Description	Type of Measure

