With regard to questionnaires, for the NIH grant we have added a few parent questionnaires. More specifically, we have included a revised version of the Parenting Stress Index (we are now using the 4th edition instead of the 3rd edition that we used on MAPS), the Social Communication Questionnaire, Attachment Q-Sort questionnaire, Beck Anxiety Inventory, Behavioral Inhibition Questionnaire, Preschool Anxiety Questionnaire, Repetitive Behavior Scale-Revised, Family Resource Scale, Parenting Scale, and Parental Flooding Scale. We have also added one teacher-report questionnaire, the Preschool Anxiety Questionnaire-teacher report version. All of these measures are psychometrically sound and have been frequently used with families of young children with developmental delays and Autism Spectrum Disorder.

b. Classification of significant change(s):

- SAFETY

1a. List any change(s) in monitoring (number each change):

1b. If any item(s) listed above DECREASE monitoring, explain why subject safety will NOT be adversely affected.

- PROCEDURES

2a. List any change(s) in subject-related intervention (number each change): None
2b. What is the scientific justification for item(s) above, and explain how risk to subjects is affected:

There is no additional risk to subjects. The changes are scientifically justified because the revised changes to the phone screen, consent, and questionnaires will more accurately identify the families eligible for this study (phone screen), provide more accurate information to participants about what the study will entail (consent), add additional psychometrically sound measures to assess the constructs of interest, and is in line with the NIH funded proposal.

SUBJECTS

3a. List any change(s) that remove exclusion criteria or broaden inclusion criteria (number each change): The study will now focus on children with Autism Spectrum Disorder specifically, rather than children with developmental delays more broadly.

3b. Justify any item(s) above that remove safety exclusion or modifies fairness in subject selection: This is what was approved by NIH for this project.

ADMINISTRATIVE

4a. Change study title of IRB approval to the following: Stress-reduction techniques for effective parenting skills (STEPS) project

4b. If study personnel will be changed, use the "Request to Change IRB Study Personnel" form.

4c. If sponsor has changed, name of sponsor is:

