If yes: "Great! Before I go over all of the study details, I would like to point out that this particular intervention is for parents of children with ASD. Is your child currently diagnosed with an autism spectrum disorder?"

Complete Section I

If yes:

"If you have a few minutes, I'd like to tell you a little more about this study. Is now a good time?"

If no:

Explain that we're only recruiting children with an ASD diagnosis at this time so they will not be eligible for the study but we plan on having more groups for parents of children with developmental delays. Ask if they would like to be placed on the waitlist to be contacted for the next study. Thank them for reaching out and for taking the time to hear about the study. After hanging up, add family to the waitlist and input all of the necessary info.

2. Brief Summary of the Intervention:

"The STEPS Project is an intervention study taking place at Loma Linda University in collaboration with Cal State Fullerton for parents of children with autism spectrum disorder. It was put in place to provide support for parents and to reduce parenting stress. Our hope is that this experience will help reduce your parenting stress, enable you to feel more confident as a parent, reduce concerns you have about your child, and in turn, improve your child's behavior.

As a part of this study, you would participate in one of two parent interventions. One intervention focuses on mindful awareness and the other is an educational parent support group. Both groups run for 8 weeks and have one 6-hour weekend event during week 6. If you choose to enroll in the program, it will be very important for you to attend all 8 intervention sessions and the weekend event. Childcare will be provided. Groups will be either Monday or Wednesday night and both will begin mid-January 2019 and end in March 2019. You will be randomly assigned to a group, like the flip of a coin. We will let you know which group you will be assigned to after your first lab assessment.

As I said, we are offering these interventions as part of a research study and therefore, in order to determine how effective the treatments are, we are asking that families participate in five lab visits for assessments. There will be two before the group begins, one immediately after the group is completed, one 6 months after the group is done, and one 12 months after the group is done.

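### Aim 4 is stated against waitlisted parents, but the 2018 phone script randomises every family to one of two concurrent active groups, so the contrast as written has no comparator arm

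*Combined protocol and SAP*

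**What the plan says.** **Objectives.** The Aim 4 hypothesis is that "Children of parents receiving MBSR will show greater reductions in behavior problems compared to children of waitlisted parents". It is the only hypothesis that names a waitlist. Aim 3 predicts better parenting behaviour "compared to controls as evidenced in observational as well as self-report measures", without saying who the controls are. Aims 2, 5 and 6 name no comparator.

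**Study Information timeline, Informed Consent Process and Procedures.** These sections contain no hypothesis, but they show how the waitlist worked. Every family receives MBSR, and chance decides when: "Parents assigned to the spring group will begin intervention in March and parents assigned to the summer intervention will begin intervention in June". The Summer group has a second baseline assessment before it starts.

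**Phone screen instructions, Brief Summary of the Intervention (2018).** Parents are randomised to one of two interventions: "One intervention focuses on mindful awareness and the other is an educational parent support group". On format, "Both groups run for 8 weeks and have one 6-hour weekend event during week 6". On timing, "Groups will be either Monday or Wednesday night and both will begin mid-January 2019 and end in March 2019". Section VII of the Phone Screening Form adds that both groups meet from 6 to 8 pm. Assessments after the group are immediate, at 6 months and at 12 months.

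**Change Request Form (2018).** The form refers to revised aims when it explains the new consent form. Under Procedures it reads "2a. List any change(s) in subject-related intervention (number each change): None".

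**Data Analysis.** The example given for child behaviour problems is a dependent-sample t-test. **Subject Recruitment & Screening** says that 70 families give power of 0.80 for a medium effect. It names no comparator, test or alpha.

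**The concern.** The comparator defines what a randomised trial estimates. Against families who are waiting, a difference in child behaviour includes whatever comes from meeting weekly with other parents, being attended to and having childcare. Against a group on a similar schedule, much of that is present in both arms. These are two different questions, and the supplied text states the first while the script sets up the second.

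If this is left as it stands, a positive result from the 2018 arms could be reported under Aim 4 as an effect over no treatment. A null result could be read as MBSR doing no better than waiting. Neither conclusion would follow. Aim 4 is also the only between-arm hypothesis about children, and the title on the cover is about improving outcomes for children.

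**Working it through.** **1. Set the two designs side by side.**

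| | Protocol text (2011–12) | Phone script (2018) |
|---|---|---|
| What is randomised | When MBSR is given | Which group is attended |
| Arm A | MBSR, March–April 2012 | Mindful awareness, mid-January to March 2019 |
| Arm B | MBSR, June–July 2012 (waits first) | Educational parent support group, mid-January to March 2019 |
| Untreated randomised arm at the first post-intervention comparison | Yes: Summer, second baseline in June 2012 | None |

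**2. Check whether the script contains a waitlist under another name.** It uses the word several times, always for a recruitment list. That list holds families without an autism diagnosis, children who are too young, parents below the stress cutoff, and parents who cannot attend on both evenings. None of these families is randomised, so none can supply the Aim 4 comparator.

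**3. Control-arm contact before the comparison.**
- Protocol: the Summer group has 0 hours of group contact before its June 2012 assessment.
- Script: 8 sessions × 2 h + 6 h = 22 h. The sessions and the weekend event come from the Brief Summary, and the 2-hour length from the 6–8 pm times in section VII.

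**4. Check the time points.** Aim 4 covers post-intervention and follow-up. Under the 2011–12 schedule, follow-up was in November 2012 (Spring) and February 2013 (Summer), after the Summer group had been treated in June–July 2012. Even then the waitlist contrast existed only at the first post-intervention comparison. Under the script it exists at no time point.

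**5. See whether the sample size statement settles the comparator.** The dropout figure is consistent: 90 × (1 − 0.20) = 72, given as about 70. The documents do not define a medium effect or give alpha. I assume a standardised difference d = 0.5 (or f² = 0.15 for regression) and two-sided alpha of 0.05.
- Two arms of 35: power = Φ(d√(n/2) − 1.96) = Φ(0.5 × √17.5 − 1.96) = Φ(0.13) = 0.55.
- Two arms of 35, adjusted for a baseline correlated 0.67 with the outcome: the SD is multiplied by √(1 − 0.67²) = 0.742, so power = Φ(2.092/0.742 − 1.96) = 0.80.
- Paired t-test within one arm of 35: 0.82.
- Paired t-test on all 70: 0.98.
- Regression with two predictors, N = 70: 0.82.

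Several unstated set-ups give about 0.80, some between arms and some not. The statement therefore does not show which contrast, or which control, the medium effect refers to.

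**6. Check the analysis.** A dependent-sample t-test measures change within a group. It does not test either version of a between-arm Aim 4.

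**The case against.** The strongest reply is that the first part of the document is the 2011–12 MAPS protocol, while the trial now recruiting is its successor under a new title and a grant. The change request says that revised aims exist. They may be set out properly in grant or consent text that is not available here. That stands as a limit: the finding concerns the supplied objectives, design and analysis text, and does not show that the investigators have no aims for an active comparator. It does not remove the finding. The cover puts the 2018 date and the autism title directly above these objectives, and nothing supplied replaces them.

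It is also fair to say that an active control is a legitimate choice. The point is the mismatch, not the choice.

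A reader might infer more than the documents support:

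- *That answering None at item 2a was wrong.* The item reports changes from the version approved just before, which is not shown. The form says the stress index replaces a Perceived Stress Scale in the phone screen, yet the protocol text never mentions that scale. Intermediate changes are therefore plausible, and the support group may already have been approved.
- *That the arms differ only in mindfulness content.* The script matches weeks, weekend event and evening hours. It does not describe the support group's curriculum, leader or homework, whereas MBSR in the protocol includes daily home practice.
- *That the medium effect was derived against a waitlist, or that a specific smaller effect should now be expected.* The documents tie it to no comparator and give no figure for non-specific group benefit.
- *That support-group parents will never be offered MBSR.* The script is silent, and the consent form is not available.

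**Conclusion.** The point holds as a contradiction between the stated hypothesis and the arms described to parents. Aim 4 needs a waiting arm, and the 2018 script has none, so the contrast as written cannot be estimated. In the control arm, contact before the comparison moves from 0 to about 22 hours, taking sessions as 2 hours. The size of any change in the expected treatment difference cannot be derived from the documents, and none is claimed.

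The verdict rests on two assumptions: that the script describes the trial being run, and that no text outside the supplied document has already restated Aim 4. If revised aims do exist elsewhere, the task becomes bringing this document into line with them. Only Aim 4 is contradicted outright. Aim 3 is undefined, since its controls could be either kind.

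**What to change.** Reconcile the objectives, design, sample size and analysis sections with the phone script, and state one control condition. If the script's two groups are what is run:

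- Reword the Aim 4 hypothesis as MBSR versus educational parent support group at post-intervention, 6 months and 12 months. Define the controls in Aim 3 in the same way.
- In Data Analysis, replace the dependent-sample t-test for child behaviour with a between-arm comparison at those time points.
- State that the result is the effect of MBSR relative to an active support group on a similar schedule, not relative to no treatment. Do not claim that only the mindfulness content differs.
- State whether the medium effect in Subject Recruitment & Screening is still the expected difference against an active control, and for which test.
- Confirm the item 2a answer against the previously approved version. No correction can be called for from the text supplied.

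The cost is amendment wording only, and the document date of July 2018 leaves time before groups begin in mid-January 2019. The price is a narrower claim: the trial would no longer speak to MBSR against waiting.
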